### **9.1.2. Serious Adverse Events (SAEs)**

A serious adverse event (SAE) is an untoward medical occurrence or effect associated with the use of a study drug at any dose, regardless of whether it is considered to be related to the study drug, which results in one of the following:

- Death (ie, all deaths on treatment or within 4 weeks after last ataluren administration), including deaths due to disease progression. Any death occurring later than 4 weeks following the last dose need not be reported as a serious adverse event unless it is a result of an event that started within the period covered by the on-study definition. The reported adverse event should be the event that caused the death. In addition, any adverse event resulting in death that occurs subsequent to the adverse event-reporting period and that the investigator assesses as possibly related to ataluren should also be reported as serious.
- Life-threatening adverse event. This is an event that, in the view of either the investigator or the sponsor, places the subject at immediate risk of death. It does not include an event that, had it occurred in a more severe form, hypothetically might have caused death.
- Inpatient hospitalization or prolongation of existing hospitalization (excluding hospitalizations for administration of ataluren, procedures required by the study protocol,

or CF-related diagnostic procedures; other planned hospitalizations; or hospitalizations related only to progression of disease). Please note that CF pulmonary exacerbations should be reported if they meet this criterion. Treatments in the emergency room for procedures such as hydration that do not require admitting the subject to the hospital and observational durations in the emergency room for less than 24 hours are not considered serious.

- Persistent or significant disability or incapacity or substantial disruption of the ability to conduct normal life functions.
- Any other medically important event that the investigator or the sponsor judges to be serious or which is defined as serious by the regulatory agency in the local country. Medical judgment should be exercised in deciding whether a reaction is serious in other situations. Important medical events that do not result in death, are not immediately life-threatening, and do not require hospitalization may be considered serious when, based on appropriate medical judgment, they may jeopardize the subject and may require medical or surgical intervention to prevent any of the outcomes listed above. Examples of such medical events include allergic bronchospasm requiring intensive treatment administration in an emergency room or at home, newly diagnosed malignancy, or blood dyscrasias, or convulsions that do not result in inpatient hospitalization, or the development of drug dependency or drug abuse.
- A pregnancy resulting in spontaneous abortion, stillbirth, neonatal death, or congenital anomaly (including that in an aborted fetus).

Except for CF pulmonary exacerbations, an event need not be reported as a SAE if it exclusively represents a relapse or an expected change or progression of the baseline CF unless hospitalization is required. This type of event need only to be reported as an adverse event.

Note that any SAEs occurring within 4 weeks of the date of last dose should be reported to the CRO Pharmacovigilance Unit if the investigator becomes aware of them.

In addition to serious adverse events, adverse events of special interest must be reported to the CRO Pharmacovigilance Unit within 24 hours. Adverse events of special interest include the following:

Laboratory abnormalities:

- Serum cystatin C  $>1.33 \times \text{ULN}$
- Serum creatinine  $> \text{ULN}$  for age
- Serum BUN  $>1.5 \times \text{ULN}$
- Urine dipstick with  $\geq 2+$  blood
- Urine dipstick with  $\geq 2+$  protein

Signs/symptoms:

- Dysuria
- Flank (renal) pain
- Nephrolithiasis or other urinary tract calculi

It should be noted that laboratory data sent to and analyzed by the Central Laboratory need not be reported through the CRO Pharmacovigilance Unit as these data will already be reported to PTC Therapeutics. Only those laboratory abnormalities meeting the protocol-defined criteria of an adverse event (ie, those that require clinical intervention or further investigation (beyond ordering a repeat [confirmatory] test), see [Section 9.1.1](#)) should be reported as adverse events in the appropriate CRF, whether they were analyzed by the Central Laboratory or another laboratory.

### **9.1.3. Unexpected Adverse Events**

Unexpected adverse events are defined as those events that were not previously reported with ataluren as referenced in the most current investigator brochure, or that are symptomatically and pathophysiologically related to a known toxicity but differ because of greater severity or specificity. For example, under this definition, hepatic necrosis would be unexpected (by virtue of greater severity) if the investigator brochure only referred to elevated hepatic enzymes or hepatitis. Similarly, cerebral thromboembolism and cerebral vasculitis would be unexpected (by virtue of greater specificity) if the investigator brochure only listed cerebral vascular accidents. “Unexpected,” as used in this definition, also refers to an adverse event that is mentioned in the most current investigator brochure as occurring with the class of drugs or as anticipated from the pharmacological properties of ataluren, but is not specifically mentioned as occurring with the medicinal product.

For the purposes of considering expectedness, the ataluren investigator brochure provides a summary of the safety profile of ataluren based on available clinical information (also referred to as the reference safety information).

## **9.2. Eliciting Adverse Event Information**

Each study subject will be questioned about adverse events at each study visit or during any telephone contact with the subject or parent/guardian caregiver. The investigator is to report all directly observed adverse events and all adverse events spontaneously reported by the subject/caregiver at each scheduled clinic visit after ataluren administration or during any telephone contact with the subject/caregiver. The type of question asked should be open-ended, eg, “*How have you/your child been feeling?*” or a similar type of query.

## **9.3. Adverse Event Recording**

All adverse events (both serious and non-serious) that occur in subjects during the adverse event reporting period must be recorded, whether or not the event is considered drug related. In addition, any non-serious, known untoward event that occurs subsequent to the adverse event reporting period that the investigator assesses as possibly related to the investigational drug/product should also be recorded as an adverse event.

All adverse events are to be recorded in the source documents and CRF using concise medical terminology; whenever possible terms contained in Medical Dictionary for Regulatory Activities (MedDRA) should be employed. In addition, the following information should be recorded:

- Indication of whether the event is serious or non-serious (see [Section 9.1](#))
- Relationship to ataluren (see [Section 9.4](#))
- Severity of the event (see [Section 9.5](#))

- Onset date
- Resolution date, or date of death
- Action taken
- Outcome of the event

Classification of the event as serious or non-serious determines the reporting procedures to be followed.

#### 9.4. Describing Adverse Event Relationship to Study Drug

Based on the considerations outlined in [Table 4](#), the investigator should provide an assessment of the relationship of the adverse event to the study drug, ie, whether there is a reasonable possibility that the study drug caused the adverse event.

**Table 4: Relationship of Ataluren to Adverse Event**

Relationship	Description
Probable	A clinical event in which a relationship to ataluren seems probable because of such factors as consistency with known effects of the drug; a clear temporal association with the use of the drug; improvement upon withdrawal of the drug; recurrence upon rechallenge with the drug; lack of alternative explanations for the event.
Possible	A clinical event occurring coincident with administration of ataluren and which may or may not be explained by concurrent disease or other drugs or chemicals. Information on drug withdrawal or rechallenge may be lacking.
Unlikely	A clinical event with a temporal relationship to ataluren exposure that does not preclude causality but for which there is a clear alternate cause that is more likely to have caused the adverse event than study drug. Such alternatives include a concomitantly administered drug, the subject's disease state, other medical conditions, or environmental factors.
Unrelated	A clinical event, for which a relationship to ataluren seems improbable because of factors such as inconsistency with known effects of the ataluren, lack of a temporal association with ataluren administration, lack of association of the event with ataluren withdrawal or rechallenge, and/or presence of alternative explanations for the event. Alternative explanations might include a known relationship of the adverse event to a concomitant drug, medical history of a similar event, the subject's disease state, other medical conditions, or environmental factors.

#### 9.5. Grading of Adverse Event Severity

The severity of adverse events will be graded using the CTCAE, Version 3.0 (refer to [http://ctep.cancer.gov/protocolDevelopment/electronic\\_applications/docs/ctcae3.pdf](http://ctep.cancer.gov/protocolDevelopment/electronic_applications/docs/ctcae3.pdf)). For each episode, the highest severity grade attained should be reported.

If a CTCAE criterion does not exist, the investigator should use the grade or adjectives: Grade 1 (mild), Grade 2 (moderate), Grade 3 (severe), Grade 4 (life-threatening), or Grade 5 (fatal) to describe the maximum intensity of the adverse event. For purposes of consistency with the CTCAE, these intensity grades are defined in [Table 5](#).

**Table 5: Grading of Adverse Event Severity**

Grade	Adjective	Description
Grade 1	Mild	Sign or symptom is present, but it is easily tolerated, is not expected to have a clinically significant effect on the subject's overall health and well-being, does not interfere with the subject's usual function, and is not likely to require medical attention.
Grade 2	Moderate	Sign or symptom causes interference with usual activity or affects clinical status, and may require medical intervention.
Grade 3	Severe	Sign or symptom is incapacitating or significantly affects clinical status and likely requires medical intervention and/or close follow-up.
Grade 4	Life-threatening	Sign or symptom results in a potential threat to life.
Grade 5	Fatal	Sign or symptom results in death.

Note the distinction between the seriousness and the severity of an adverse event. Severity is a measure of intensity; thus, a severe reaction is not necessarily a serious reaction. For example, a headache may be severe in intensity, but would not be classified as serious unless it met one of the criteria for serious events listed in [Section 9.1.2](#).

## 9.6. Pregnancy

PTC Therapeutics should be notified in the event that a female subject in the study becomes pregnant at any time after the subject's first dose of ataluren. Any such pregnancy occurring on-study or within 60 days of the last administration of ataluren must be reported on a Pregnancy Notification Form). This must be done whether or not an adverse event has occurred and within 24 hours of awareness of the pregnancy. The information submitted should include the anticipated date of birth or pregnancy termination.

If possible, the investigator should follow the subject until completion of the pregnancy and notify the PTC Therapeutics medical monitor of the outcome within 5 days or as specified below. The investigator will provide this information as a follow up to the initial Pregnancy Notification Form via the Pregnancy Outcome Form

If the outcome of the pregnancy meets the criteria for immediate classification as a serious adverse event (ie, spontaneous abortion, stillbirth, neonatal death, or congenital anomaly [including that in an aborted fetus]), the investigator should follow the procedures for reporting serious adverse events, ie, report the event to the CRO Pharmacovigilance Unit and follow up by submission of appropriate adverse event CRFs (see [Section 9.9](#)).

## 9.7. Follow-Up of Unresolved Adverse Events

All adverse events should be followed up by the investigator until they are resolved, or the investigator assesses them as chronic or stable. Follow-up of any SAE that is fatal or life-threatening should be provided within one additional calendar week. The investigator should consider protocol guidelines and use his/her discretion in ordering additional tests as necessary to monitor the resolution of such events. In the event of additional investigations, the CRO Pharmacovigilance Unit should be informed via e-mail or fax. A subject withdrawn from the study because of an adverse event must be followed by the investigator until clinical recovery is complete and laboratory results have returned to normal, or until progression has been stabilized. Follow-up may need to continue after the subject has discontinued from the study, and additional investigations may be requested by the medical monitoring team.

## 9.8. Adverse Event Reporting Period

The first day of adverse event reporting will coincide with the day the first dose of ataluren is administered. The adverse event reporting period for this study ends with the 4-Week ( $\pm$  7 days) Post-Treatment Follow-up visit, except as described in [Section 9.7](#). In addition, SAEs occurring in a subject after the study period should be reported to the sponsor if the investigator becomes aware of them.

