## 4.2. Inclusion Criteria

Subjects must meet all of the following conditions to be eligible for enrollment into the study:

1. Evidence of signed and dated informed consent/assent document(s) indicating that the subject (and/or parent/legal guardian) has been informed of all pertinent aspects of the trial. **Note: If the study candidate is considered a child under local regulation, a parent or legal guardian must provide written consent prior to initiation of study screening procedures and the study candidate may be required to provide written assent. The rules of the responsible Institutional Review Board/Independent Ethic Committee (IRB/IEC) regarding whether one or both parents must provide consent and the appropriate ages for obtaining consent and assent from the subject should be followed.**
2. Evidence of completed participation in the double-blind study, PTC124-GD-009-CF (Study 009).
3. Body weight  $\geq 16$  kg.
4. Performance of a valid, reproducible spirometry test using the study-specific spirometer during the screening period. **Note: An FEV1 value within a pre-specified range is not required for eligibility.**
5. Confirmed screening laboratory values within the central laboratory ranges. **Note: Confirmation should be performed for out-of-range values during the screening period to determine if the abnormality is real or artifactual. Values used to establish eligibility should be obtained during the screening period, and should generally be the most recent measurement obtained. All screening laboratory results must be received, reviewed and deemed acceptable for study participation before a subject is enrolled into the study.**
6. In male and female subjects who are sexually active, willingness to abstain from sexual intercourse or employ a barrier or medical method of contraception during the study drug administration and 60-day follow-up period.
7. Willingness and ability to comply with all study procedures and assessments, including scheduled visits, drug administration plan, laboratory tests, and study restrictions. **Note: The Investigator should consider any psychological, social, familial, or geographical factors that might preclude adequate study participation.**

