#### **8.2.2.2. Post-Treatment Visits**

All subjects, including those who discontinue study drug prematurely, will return to the investigational site 4 weeks ( $\pm 7$  days) after the last dose of ataluren for a 4-Week Post-Treatment Follow-up Visit. Please refer to [Section 10](#) for further details regarding subject withdrawal procedures. The end of trial will be defined as the date the last subject completes the last study visit, which is expected to be the 4-Week Post-Treatment Follow-up Visit.

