### **11.4.5. Primary Variables**

#### **11.4.5.1. Adverse Events**

Adverse events will be classified using the MedDRA classification system. The severity of adverse events will be graded by the investigator according to the CTCAE, Version 3.0 whenever possible. A treatment-emergent adverse event is defined as an adverse event that occurs or worsens in the period extending from the day of a subject's first ataluren dose in this study to 4 weeks after the last ataluren dose in this study.

The frequency of subjects experiencing a specific adverse event will be tabulated by treatment group, body system, and MedDRA term. In the by-subject analysis, a subject having the same event more than once will be counted only once. Adverse events will be summarized by worst CTCAE grade.

Adverse events classified as CTCAE Grade 3 or higher; study-drug-related events; adrenal, hepatic, and renal events leading to special diagnostic evaluations; events leading to discontinuation from treatment; and SAEs will be considered with special attention.

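### An early post-treatment visit leaves 1 to 7 days of the 28-day TEAE window, and any visit inside the permitted window leaves 25 to 39 days of the 60-day pregnancy window, with no scheduled contact

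*Protocol*

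**What the plan says.** Four sets of provisions bear on follow-up after the last dose.

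- **Adverse event collection.** Protocol 9.8: "The adverse event reporting period for this study ends with the 4-Week" post-treatment visit, with ±7 days. Protocol 8.2.2.2 ties that visit to dosing: subjects return 4 weeks ±7 days "after the last dose of ataluren for a 4-Week Post-Treatment Follow-up Visit". It also closes the study there: "The end of trial will be defined as the date the last subject completes the last study visit", which is expected to be this one. Table 3 lists nothing after Visit 15.
- **Treatment-emergent window.** Protocol 11.4.5.1 runs it from the first dose "to 4 weeks after the last ataluren dose in this study". SAP 4.10.1 uses the same limit.
- **Pregnancy.** Inclusion criterion 6 (protocol 4.2) requires abstinence or contraception "during the study drug administration and 60-day follow-up period". Protocol 9.6: "Any such pregnancy occurring on-study or within 60 days of the last administration of ataluren must be reported". Under protocol 8.2.7.1 and Table 3, β-HCG is measured only at study visits, the last being Visit 15.
- **Late deaths and SAEs.** Protocol 9.1.2: "Any death occurring later than 4 weeks following the last dose need not be reported as a serious adverse event", with exceptions for events that began on study and for events judged possibly related. Protocol 9.8: "SAEs occurring in a subject after the study period should be reported to the sponsor if the investigator becomes aware of them".

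**The concern.** The window in which an event counts and the period in which events are sought should have the same end. Here both are nominally four weeks, but one is fixed at day 28 and the other moves with the visit. A subject seen on day 21 is asked about 21 of the 28 days that the primary safety analysis covers, and a subject seen on day 28 about all of them. Capture then depends partly on scheduling. The exposure-adjusted rate in SAP 4.10.1 divides events by days on study drug, so an event missed after an early visit lowers the numerator and leaves the denominator unchanged.

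For pregnancy, two sections rely on a 60-day period that the schedule does not contain. Reporting is mandatory once a pregnancy is known, but nothing planned after the 4-week visit would bring it to light. Some pregnancy outcomes are themselves SAEs under 9.1.2 and 9.6, so an unreported pregnancy can also hide an SAE.

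The wording on late deaths and SAEs raises a smaller question: a site has to work out which section governs.

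**Working it through.** **Inputs**

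- Nominal interval from end of treatment to follow-up visit: Study Day 1344 to Study Day 1372 (protocol Table 3).
- Visit tolerance: ±7 days, counted from the last dose (protocol 8.2.2.2).
- Treatment-emergent window: 28 days after the last dose (protocol 11.4.5.1, SAP 4.10.1).
- Pregnancy window: 60 days after the last dose (protocol 9.6; inclusion criterion 6).

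**Plan's own figure.** 1372 − 1344 = 28 days = 4 weeks. It reproduces.

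**Permitted visit days.** V = 28 ± 7, so V runs from 21 to 35.

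**Days without scheduled contact.** Treatment-emergent gap = max(0, 28 − V). Pregnancy gap = 60 − V.

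| Visit day V | Treatment-emergent gap (days) | Share of 28 days | Pregnancy gap (days) | Share of 60 days |
|---|---|---|---|---|
| 21 | 7 | 25% | 39 | 65% |
| 24 | 4 | 14% | 36 | 60% |
| 27 | 1 | 4% | 33 | 55% |
| 28 | 0 | 0% | 32 | 53% |
| 35 | 0 | 0% | 25 | 42% |

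**Typical size of the treatment-emergent gap.** The documents do not give the distribution of visit days. If it were uniform over the 15 permitted days (an assumption), 7 of 15 days would leave a gap, and the mean gap would be (7+6+5+4+3+2+1)/15 = 28/15 = 1.9 days. The possible range per subject is 0 to 7 days.

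**What still operates in the gap.** SAEs within 4 weeks of the last dose are reportable if the investigator becomes aware of them (9.1.2), and later SAEs likewise (9.8). New non-serious events are recorded if they are known and judged possibly related (9.3). Events already open are followed to resolution or stability (9.7). The days in the gap are therefore covered passively. What can be lost is a new non-serious event that is judged unrelated or never becomes known, or an SAE that never reaches the investigator.

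**Late deaths.** Take a death in week 6 after the last dose, from an event that began after week 4 and is judged unrelated. Under 9.1.2 it need not be reported as an SAE. Under 9.8, an SAE that the investigator learns of after the study period should go to the sponsor. If 9.1.2 is read as defining what counts as an SAE, 9.8 does not reach this death. If 9.8 is read as the reporting rule for every later SAE, it does. Neither section says which reading applies.

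**The case against.** The strongest reply is that the follow-up visit is designed for day 28, which closes the treatment-emergent window exactly, and that half the tolerance goes beyond it. Subjects whose last dose was at least 4 weeks before discontinuation attend only the follow-up visit (8.2.2.1) and so have no treatment-emergent gap. After an adverse event discontinuation, follow-up continues to about 4 weeks or to recovery or stabilisation, whichever is later (6.3.4). Seven days is about 0.5% of the planned 1372 days (7/1372), there is no control arm, and SAP 4.2 calls all analyses descriptive. All of this stands, and it makes the first gap small. It does not explain why the two limits differ when matching them costs almost nothing.

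On pregnancy, 9.6 works on awareness, and the 60 days can be read as a contraception and reporting period rather than a testing schedule. Protocol 14.1.5 calls the restriction a general precaution, given the nonclinical findings and the sexual immaturity of many likely subjects. That supports a low risk. It leaves a mandatory 60-day report, and a named follow-up period, with no contact behind them.

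Several stronger readings are tempting but not supported:

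- *Safety follow-up always ends before the 28-day window closes.* It does so only for visits on days 21 to 27.
- *Pregnancies after the visit cannot be found.* They can be, through spontaneous reports; only scheduled ascertainment is absent.
- *Conceptions shortly before the last test are missed as well.* That depends on test performance, which the documents do not give.
- *The sponsor's early termination (SAP 2.1) makes the gap general.* Subjects pass through this visit in any case, and nothing indicates that visits after the termination would be early.
- *Partner pregnancies should be covered because criterion 6 also binds male subjects.* Protocol 9.6 concerns female subjects only and no section promises partner reporting, so that would be a separate design choice.
- *Sections 9.1.2 and 9.8 flatly contradict each other.* They can be read as a definition followed by a reporting rule; the defect is ambiguity.

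**Conclusion.** The point holds in two parts of different weight. For treatment-emergent events, 1 to 7 of the 28 post-treatment days (at most 25%, and only for a day-21 visit) have passive capture alone when the visit is on days 21 to 27. The gap is zero from day 28 onward. For pregnancy, the gap exists at every visit held within the permitted window: 39, 32 or 25 of the 60 days for a visit on day 21, 28 or 35. The wording on late deaths and SAEs needs clarifying, but no misreporting is shown.

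These figures count the ±7 days from the last dose, as 8.2.2.2 states. They say nothing about how many events or pregnancies would be missed, which the documents do not allow one to estimate. No sample size, power or significance level depends on them. The case for acting is that the protocol's own windows can be matched at very little cost.

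**What to change.** 1. Either end the adverse event reporting period (9.8) at the later of the post-treatment visit and day 28 after the last dose, or set the visit window to 28 days with 0/+7. The second closes the gap by itself. The first needs a short call on or after day 28 for anyone seen earlier. Make 8.2.2.2, 8.2.12 and Table 3 agree.
2. Add one phone contact at about day 60 after the last dose, asking female subjects of childbearing potential about pregnancy, so that the 60-day period in criterion 6 and 9.6 exists in the schedule. Say in 8.2.2.2 whether the end of trial includes this call.
3. Reconcile 9.1.2 and 9.8 so that sites have one stated rule for deaths and other SAEs later than 4 weeks after the last dose.

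The cost is wording, one call per relevant subject, and a short call after an early visit if the first option is chosen. No clinic visit or procedure is added. The downside is that pregnancy data collection ends 60 − 28 = 32 days after the nominal visit, between four and five weeks later than now.
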